**Figure 1-1. Cohorts 1, 2, and 3 Study Schema**

Each of the three cohorts will consist of two groups:

- **Group 1** (test, N = 10): Subjects with mild/moderate/severe hepatic impairment
- **Group 2** (reference, N = 10): Subjects with normal hepatic function

Safety will be evaluated by assessment of physical examinations, vital signs, clinical laboratory tests and ECGs at various time points during the study, and by documentation of AEs.

### **PK Assessments**

#### **Plasma PK Collection**

Intensive PK sampling will occur relative to dosing of GS-9674 at the following time points for each cohort:

- **Day 1:** -0.5, 0 (pre-dose,  $\leq 5$  minutes prior to dosing), 0.25, 0.5, 1, 1.5, 2, 2.5, 3, 3.5, 4, 5, 6, 8, 10, 12, 16, 24, 48, 72, and 96 hours post-dose

Plasma concentrations of GS-9674 (and its metabolites, as applicable) will be determined and PK evaluated. PK parameters will be estimated, as appropriate.

In addition, on Day 1 at the 3 and 5 hours post dose time-points, additional plasma samples will be collected for plasma protein binding evaluation. Alternatively, pre-dose samples may be utilized for plasma protein binding evaluation.

A blood sample for PK analysis will also be collected at the Early Termination (ET) visit (if applicable) and may be analyzed.

## **PD Assessments**

### **Plasma and/or Serum PD Collection**

Blood samples will be collected relative to dosing of GS-9674 or PTM to measure PD biomarkers including but not limited to FGF19 (fibroblast growth factor 19) and 7-alpha-hydroxy-4-cholesten-3-one (C4) for GS-9674 at the following time points for each cohort:

- **Day -1:** -0.5, 0 (predose,  $\leq 5$  minutes prior to dosing), 0.25, 0.5, 1, 1.5, 2, 2.5, 3, 3.5, 4, 4.5, 5, 6, 8, 10, 12, and 16 hours post-dose (relative to Day 1 dosing time)
- **Day 1:** -0.5, 0 (pre-dose,  $\leq 5$  minutes prior to dosing), 0.25, 0.5, 1, 1.5, 2, 2.5, 3, 3.5, 4, 5, 6, 8, 10, 12, 16, 24, 48, 72, and 96 hours post-dose

A single blood sample will be collected for analysis including but not limited to bile acids at the following time point:

- **Day 1:** -0.5 hours predose

A blood sample for PD analysis will also be collected at the ET visit (if applicable) and may be analyzed.

## **Safety Assessments**

- Complete Physical exam: Screening and ET visit (if applicable)
- Symptom-directed physical exam: Days -2, 5, and FU visit
- Vital signs (blood pressure, pulse, respiration rate, and temperature): Screening, Days -2, 1 (predose and at approximately 3 hours postdose), 5, and FU visit or ET visit (if applicable)
- Height, Weight, and BMI: Screening
- Clinical Laboratory Tests (hematology, fasting chemistry, and urinalysis): Screening, Days -2 (two sets of safety labs will be collected upon clinic admission; one will be sent to the central lab and another will be sent to the sites' local lab to obtain results in time for enrollment on Day 1), 5, and FU visit or at ET visit (if applicable)
- Coagulation (PT, PTT, INR): Screening and FU Visit

- Urine drug/alcohol assessment: Screening, Day -2, and at the FU visit or at ET visit (if applicable).
- 12-lead ECG: Screening, Days -2, 5, and at the FU visit or ET visit (if applicable)
- Serum Pregnancy Test (female subjects of childbearing potential): Screening
- Urine Pregnancy Test (female subjects of childbearing potential): Days -2, 5, and at the FU visit or at ET visit (if applicable)
- FSH (female subjects  $\leq$  54 years old with amenorrhea  $>$  12 months): Screening
- Serology (Hepatitis B surface antigen [HBVsAg], Hepatitis C antibody [HCV-Ab], Human immunodeficiency virus [HIV]-1/2): Screening
- Assessment of AEs and concomitant medications will continue throughout the study.

Additional details regarding study assessments can be found in Section 13.

#### **1.4. Sample Size and Power**

For each cohort, with 16 (8 per group) evaluable subjects, the estimated upper limit of one-sided 95% confidence intervals (CIs) of the geometric least squares mean (GLSM) ratio of (mild, moderate or severe) hepatic impaired group vs. control (normal hepatic function), with regards to  $AUC_{last}$ ,  $AUC_{inf}$ , and  $C_{max}$ , would be less than 200% with  $\geq$  88% probability, if the estimated GLSM ratio were 1.0. This is assuming a standard deviation (SD) of no more than 0.463 on a natural logarithm scale, supported by previous Gilead study GS-US-402-1851. With 25% overage, a total sample size of 60 subjects (10 per group, 20 per cohort) will be required.

## **2. TYPE OF PLANNED ANALYSIS**

### **2.1. Data Monitoring Committee Analyses**

This study does not have a data monitoring committee (DMC). Therefore, no analyses will be conducted for the DMC.

### **2.2. Interim Analysis**

No interim analysis is planned.

### **2.3. Final Analysis**

After all subjects have completed the study, outstanding data queries have been resolved or adjudicated as unresolvable, and the data have been cleaned and finalized, the final analysis of the data will be performed.

### **2.4. Changes from Protocol-Specified Analysis**

No changes from protocol-specified analyses are planned.

### **3. GENERAL CONSIDERATIONS FOR DATA ANALYSES**

Analysis results will be presented using descriptive statistics. For categorical variables, the number and percentage of subjects in each category will be presented; for continuous variables, the number of subjects (n), mean, SD or standard error (SE), median, first quartile (Q1), third quartile (Q3), minimum, and maximum will be presented.

By-subject listings will be presented for all subjects in the All Enrolled Analysis Set, and sorted by subject identification (ID) number in ascending order, visit date, and time (if applicable), unless otherwise specified. Data collected on log forms, such as AEs, will be presented in chronological order within subject. The treatment group to which subjects were initially assigned will be used in the listings. Age, sex at birth, race, and ethnicity will be included in the listings, as space permits.

#### **3.1. Analysis Sets**

Analysis sets define the subjects to be included in an analysis. Analysis sets and their definitions are provided in this section. The analysis set will be identified and included as a subtitle of each table, figure, and listing.

For each analysis set, the number and percentage of subjects eligible for inclusion will be provided in the disposition table as detailed in Section 4. A listing of reasons for exclusion from analysis sets will be provided by subject.

##### **3.1.1. All Enrolled Analysis Set**

The All Enrolled Analysis Set includes all subjects who received a study subject identification number in the study after screening.

This is the primary analysis set for safety listings.

##### **3.1.2. Safety Analysis Set**

The Safety Analysis Set includes all subjects who took at least 1 dose of study drug. This is the primary analysis set for safety analyses.

##### **3.1.3. Pharmacokinetic Analysis Sets**

The Pharmacokinetic (PK) Analysis Sets will include all enrolled subjects who took at least 1 dose of study drug and have at least 1 nonmissing postdose concentration value reported by the PK laboratory for the corresponding analytes. These are the primary analysis sets for all PK analyses.

### **3.1.4. Pharmacodynamic Analysis Sets**

The Pharmacodynamic (PD) Analysis Sets will include all enrolled subjects who received at least 1 dose of study drug and have at least 1 nonmissing PD value for each respective PD parameter.

### **3.2. Strata and Covariates**

This study does not use a stratified randomization schedule in enrolling subjects. No covariates will be included in the analyses.

### **3.3. Examination of Subject Subsets**

There are no prespecified subject subsets for analyses.

### **3.4. Multiple Comparisons**

All endpoint tests will be done at the significance level of 0.05 with no multiplicity adjustments made for testing.

### **3.5. Missing Data and Outliers**

#### **3.5.1. Missing Data**

In general, missing data will not be imputed unless methods for handling missing data are specified. Exceptions are presented in this document.

The handling of missing or incomplete dates for AE onset is described in Section [7.1.6.2](#).

#### **3.5.2. Outliers**

Outliers of non-PK data will be identified during the data management and data analysis process, but no sensitivity analyses will be conducted. All data will be included in the data analysis.

### **3.6. Data Handling Conventions and Transformations**

In general, age (in years) on the date of the first dose of study drug will be used for analyses and presentation in listings. If an enrolled subject was not dosed with any study drug, the enrollment date will be used instead of the first dosing date of study drug. If only the birth year is collected on the CRF, “01 July” will be used for the unknown birth day and month for the purpose of age calculation. If only birth year and month are collected, “01” will be used for the unknown birth day.

Non-PK data that are continuous in nature but are less than the lower limit of quantitation (LOQ) or above the upper LOQ will be imputed as follows:

- A value that is 1 unit less than the lower LOQ will be used to calculate descriptive statistics if the datum is reported in the form of “< x” (where x is considered the lower LOQ). For example, if the values are reported as < 50 and < 5.0, values of 49 and 4.9, respectively, will be used to calculate summary statistics. An exception to this rule is any value reported as < 1 or < 0.1, a value of 0.9 or 0.09, respectively, will be used to calculate summary statistics.
- A value that is 1 unit above the upper LOQ will be used to calculate descriptive statistics if the datum is reported in the form of “> x” (where x is considered the upper LOQ). Values with decimal points will follow the same logic as the bullet point above.
- The LOQ will be used to calculate descriptive statistics if the datum is reported in the form of “≤ x” or “≥ x” (where x is considered the lower LOQ, or upper LOQ respectively).

If methods based on the assumption that the data are normally distributed are not adequate, analyses may be performed on transformed data or nonparametric analysis methods may be used, as appropriate.

Natural logarithmic transformation will be used for analyzing concentrations and PK parameters. Concentration values that are below the limit of quantitation (BLQ) will be presented as “BLQ” in the concentration data listing. Values that are BLQ will be treated as 0 at predose time points and one-half the value of the LOQ at postdose time points for summary purposes.

The following conventions will be used for the presentation of summary and order statistics:

- If at least 1 subject has a concentration value of BLQ for the time point, the minimum value will be displayed as “BLQ.”
- If more than 25% of the subjects have a concentration data value of BLQ for a given time point, the minimum and Q1 values will be displayed as “BLQ.”
- If more than 50% of the subjects have a concentration data value of BLQ for a given time point, the minimum, Q1, and median values will be displayed as “BLQ.”
- If more than 75% of the subjects have a concentration data value of BLQ for a given time point, the minimum, Q1, median, and Q3 values will be displayed as “BLQ.”
- If all subjects have concentration data values of BLQ for a given time point, all order statistics (minimum, Q1, median, Q3, and maximum) and summary statistics will be displayed as “BLQ.”

### **3.7. Visit Windows**

#### **3.7.1. Definition of Predose, Postdose and Study Day**

Predose value is defined as the last available off-treatment value collected prior to the first dose of study drug.

Postdose value is defined as any value collected after the first dose of study drug and before the date of the last dose of study drug plus 30 days.

Study Day will be calculated from the first dosing date of study drug and derived as follows:

- For postdose study days: Assessment Date – First Dosing Date + 1
- For days prior to the first dose: Assessment Date – First Dosing Date

Therefore, study day 1 is the day of first dose of study drug administration.

#### **3.7.2. Analysis Visit Windows**

The nominal visit as recorded on the CRF will be used when data are summarized by visit. Any data relating to unscheduled visits will not be assigned to a particular visit or time point and in general will not be included in summaries. However, the following exceptions will be made:

- An unscheduled visit prior to the first dose of study drug may be included in the calculation of predose value, if applicable.
- Unscheduled visits after the first dose of study drug will be included in determining the maximum postbaseline toxicity grade.
- For subjects who discontinue from the study, early termination (ET) data will be summarized as a separate visit, labeled as “Early Termination.”
- Data collected on a follow-up visit will be summarized as a separate visit, and labeled “Follow-up.”
- Data obtained after the follow-up visit or last dose date plus 30 days (whichever is later) will be excluded from the summaries, but will be included in the listings.

#### **3.7.3. Selection of Data in the Event of Multiple Records on the Same Day**

Depending on the statistical analysis method, single values may be required for each day. For example, change from predose by visit usually requires a single value.

If multiple, valid, nonmissing numeric observations exist on a day, records will be chosen based on the following rules if a single value is needed:

- For predose, the last available record on or prior to the date and time of the first dose of study drug will be selected. If there are multiple records with the same time or no time recorded on the same day, average (arithmetic or geometric mean, as appropriate) will be used for the predose value.
- For postdose visits:
  - The record closest to the nominal day for that visit will be selected.
  - If there are 2 records that are equidistant from the nominal day, the later record will be selected.
  - If there is more than 1 record on the selected day, the average will be taken, unless otherwise specified.

If multiple, valid, nonmissing categorical observations exist on a day, records will be chosen based on the following rules if a single value is needed:

- For predose, the last available record on or prior to the date and time of the first dose of study drug will be selected. If there are multiple records with the same time or no time recorded on the same day, the value with the lowest severity will be selected (eg, normal will be selected over abnormal for safety ECG findings).
- For postdose values, follow the same rules described above for postbaseline numeric observations, except that if there are multiple records on the same day, the most conservative value will be selected (eg, abnormal will be selected over normal for safety ECG findings).

## **4. SUBJECT DISPOSITION**

### **4.1. Subject Enrollment and Disposition**

A summary of subject enrollment and disposition will be provided by hepatic function group and by hepatic function group within cohort. This summary will present the number of subjects enrolled, and the number and percentage of subjects in each of the categories listed below. For the Safety Analysis Set category, the denominator for the percentage calculation will be the total number of subjects enrolled for each column. For all other categories, the denominator for the percentage calculation will be the total number of subjects in the Safety Analysis Set for each column.

- Safety Analysis Set
- PK Analysis Set for each analyte
- PD Analysis Set for each biomarker
- Completed study drug
- Did not complete study drug with reason for premature discontinuation of study drug
- Completed the study
- Did not complete the study with reason for premature discontinuation of study

In addition, the total number of subjects who were enrolled, and the number of subjects in each of the disposition categories listed above will be displayed in a flowchart.

The following by-subject listings will be provided by subject ID number in ascending order to support the above summary tables:

- Reasons for premature study drug or study discontinuation

A by-subject listing of subject disposition including cohort, hepatic function group, date of the last dose of study drug (study days), study drug completion status, reason for study drug discontinuation, study completion status, reason for study discontinuation, PK set status (indicating whether or not a subject is included in a PK analysis set), and PD set status will be provided by subject ID number in ascending order.

### **4.2. Extent of Exposure**

A subject's extent of exposure to study drug data will be generated from the study drug administration page in the eCRF. Exposure data will be listed.

### **4.3. Protocol Deviations**

A by-subject listing will be provided for those subjects who did not meet at least 1 eligibility (inclusion or exclusion) criterion. The listing will present the entry criterion (or criteria if more than 1 violation) that subjects did not meet and related comments, if collected.

Protocol deviations occurring after subjects entered the study are documented during routine monitoring. Any deviations identified will be evaluated to determine if it justifies excluding the subject from any analysis sets.

## **5. BASELINE CHARACTERISTICS**

### **5.1. Demographics**

Subject demographic variables (ie, age, sex, race, and ethnicity) will be summarized by hepatic function group and by hepatic function group within cohort using descriptive statistics for age, and using numbers and percentages of subjects for sex, race, and ethnicity. The summary of demographic data will be provided for the Safety Analysis Set.

A by-subject demographic listing, including the informed consent date, will be provided by subject identification (ID) number in ascending order.

### **5.2. Baseline Characteristics**

Baseline characteristics include body weight (in kg), height (in cm), and body mass index (BMI; in kg/m^2), calculated creatinine clearance (CLcr; in mL/min) by Cockcroft-Gault method {Cockcroft 1976}, and CPT score. These baseline characteristics will be summarized by hepatic function group and by hepatic function group within cohort using descriptive statistics for continuous variables and using number and percentage of subjects for categorical variables. For baseline body weight, height, and BMI, descriptive statistics will also be presented by sex in the same table. CPT score will be summarized for hepatic impaired subjects only by presenting the number and percentage of subjects in each score category. The summary of baseline characteristics will be provided for the Safety Analysis Set. No formal statistical testing is planned.

A by-subject listing of other baseline characteristics will be provided by subject ID number in ascending order.

### **5.3. Medical History**

Medical history data will be collected at screening and listed only. General medical history data will not be coded.

A by-subject listing of general medical history will be provided by subject ID number in ascending order. The listing will include relevant medical condition or procedure reported term, onset date, ongoing status, and resolution date (if applicable).

## **6. EFFICACY ANALYSES**

Efficacy will not be evaluated in the study.

## **7. SAFETY ANALYSES**

### **7.1. Adverse Events and Deaths**

#### **7.1.1. Adverse Event Dictionary**

Clinical and laboratory AEs will be coded using the current version of the Medical Dictionary for Regulatory Activities (MedDRA). System organ class (SOC), high-level group term (HLGT), high-level term (HLT), preferred term (PT), and lower-level term (LLT) will be provided in the AE dataset.

#### **7.1.2. Adverse Event Severity**

Adverse events are graded by the investigator as Grade 1, 2, 3, or 4 according to toxicity criteria specified in the protocol. The severity grade of events for which the investigator did not record severity will be categorized as “missing” for tabular summaries and data listings. The missing category will be presented last in the summary presentation.

#### **7.1.3. Relationship of Adverse Events to Study Drug**

Study drug related AEs are those for which the investigator selected “Related” on the AE CRF to the question of “Related to Study Treatment.” Relatedness will always default to the investigator’s choice, not that of the medical monitor. Events for which the investigator did not record relationship to study drug will be considered related to study drug for summary purposes. However, by-subject data listings will show the relationship as missing from that captured on the CRF.

#### **7.1.4. Relationship of Adverse Events to Study Procedure**

Study procedure related AEs are those for which the investigator selected “Yes” on the AE CRF to the question of “Related to Study Procedures.” Relatedness will always default to the investigator’s choice, not that of the medical monitor. Events for which the investigator did not record relationships to study procedure will be considered related to study procedure for summary purposes. However, by-subject data listings will show the relationship as missing from that captured on the CRF.

#### **7.1.5. Serious Adverse Events**

Serious adverse events (SAEs) will be identified and captured as SAEs if AEs met the definitions of SAE specified in the study protocol. SAEs captured and stored in the clinical database will be reconciled with the SAE database from the Gilead Pharmacovigilance and Epidemiology Department before database finalization.

## **7.1.6. Treatment-Emergent Adverse Events**

### **7.1.6.1. Definition of Treatment Emergent**

Treatment-emergent adverse events (TEAEs) are defined as 1 or both of the following:

- Any AEs with an onset date on or after the study drug start date and no later than 30 days after permanent discontinuation of study drug.
- Any AEs leading to premature discontinuation of study drug.

### **7.1.6.2. Incomplete Dates**

If the onset date of the AE is incomplete and the AE stop date is not prior to the first dosing date of study drug, then the month and year (or year alone if month is not recorded) of onset determine whether an AE is treatment emergent. The event is considered treatment emergent if both of the following 2 criteria are met:

- The AE onset is the same as or after the month and year (or year) of the date of first dose of study drug, and
- The AE onset date is the same as or before the month and year (or year) of the date corresponding to 30 days after the date of the last dose of study drug

An AE with completely missing onset and stop dates, or with the onset date missing and a stop date later than the date of the first dose of study drug, will be considered to be treatment emergent. In addition, an AE with the onset date missing and incomplete stop date with the same or later month and year (or year alone if month is not recorded) as the first dosing date of study drug will be considered treatment emergent.

## **7.1.7. Summaries of Adverse Events and Deaths**

Treatment-emergent AEs will be summarized based on the Safety Analysis Set.

The number and percentage of subjects who experienced at least 1 TEAE will be provided and summarized by SOC, PT, and hepatic function group as follows:

- All TEAEs
- TEAEs of Grade 3 or above
- TEAEs of Grade 2 or above
- All TEAEs by severity
- All TE treatment-related AEs

- All TE treatment-related AEs by severity
- All TEAEs related to study procedures
- All TE SAEs
- All TE treatment-related SAEs
- All TEAEs leading to premature discontinuation of study drug
- All TEAEs leading to premature discontinuation of study

A brief, high-level summary of AEs described above will be provided by hepatic function group and by the number and percentage of subjects who experienced the above AEs. All deaths observed in the study will also be included in this summary.

Multiple events will be counted only once per subject in each summary. Adverse events will be summarized and listed first in alphabetic order of SOC and then by PT in descending order of total frequency within each SOC. For summaries by severity, the maximum severity will be used for those AEs that occurred more than once in an individual subject during the study.

In addition, data listings will be provided for the following:

- All AEs, indicating whether the event is treatment emergent
- SAEs
- Deaths
- AEs leading to premature discontinuation of study drug
- AEs leading to discontinuation of study

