## 8.6. Safety Analysis

All safety data collected on or after the date that study drug was first administered up to the date of last dose of study drug plus 30 days will be summarized by hepatic function group (according to the study drug received) using safety analysis set.

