### **8.6.2. Adverse Events**

Clinical and laboratory AEs will be coded using the Medical Dictionary for Regulatory Activities (MedDRA). System Organ Class (SOC), High-Level Group Term (HLGT), High-Level Term (HLT), Preferred Term (PT), and Lower-Level Term (LLT) will be attached to the clinical database.

Adverse event data will be listed by subject. Treatment-emergent AE (TEAE), Serious TEAE, and TEAE leading to discontinuation of treatment will be summarized by hepatic function group, system organ class, and preferred term using the current version the Medical Dictionary for Regulatory Activities (MedDRA).

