#### **7.1.8. Additional Analysis of Adverse Events**

No additional analysis of adverse events is planned.

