### **7.2.1. Summaries of Numeric Laboratory Results**

Descriptive statistics will be provided by hepatic function group for each laboratory test specified in the study protocol as follows:

- Predose values
- Values at each postdose visit
- Change from predose at each postdose visit

Predose and postdose values will be defined as described in Section 3.7.1. Change from predose to a postdose visit will be defined as the visit value minus the predose value. The mean, median, Q1, Q3, minimum, and maximum values will be displayed to the reported number of digits; SD values will be displayed to the reported number of digits plus 1.

In the case of multiple values in an analysis window, data will be selected for analysis as described in Section 3.7.3.

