#### 7.2.2.2. Summaries of Laboratory Abnormalities

Laboratory data that are categorical will be summarized using the number and percentage of subjects in the study with the given response at predose and each scheduled postdose visit.

The following summaries (number and percentage of subjects) for treatment-emergent laboratory abnormalities will be provided by lab test and hepatic function group; subjects will be categorized according to the most severe postdose abnormality grade for a given lab test:

- Graded laboratory abnormalities
- Grade 3 or 4 laboratory abnormalities

For all summaries of laboratory abnormalities, the denominator is the number of subjects with nonmissing postdose values up to 30 days after last dosing date.

A by-subject listing of treatment-emergent laboratory abnormalities will be provided by subject ID number and visit in chronological order. This listing will include all test results that were collected throughout the study for the lab test of interest, with all applicable severity grades displayed.

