#### 7.3. Vital Signs

Descriptive statistics will be provided by hepatic function group for vital signs as follows:

- Predose value
- Values at each postdose visit
- Change from predose at each postdose visit

Predose and postdose values will be defined as described in Section 3.7.1. Change from predose to a postdose visit will be defined as the postdose value minus the predose value.

In the case of multiple values in an analysis window, data will be selected for analysis as described in Section 3.7.3. No formal statistical testing is planned.

A by-subject listing of vital signs will be provided by subject ID number and visit in chronological order.

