#### **7.5. Investigator Electrocardiogram Assessment**

A shift table of the investigators' assessment of ECG results at each visit compared with predose values will be presented by hepatic function group using the following categories: normal; abnormal, not clinically significant; abnormal, clinically significant; or missing. The number and percentage of subjects in each cross-classification group of the shift table will be presented. Subjects with a missing value at predose or postdose will not be included in the denominator for percentage calculation. No formal statistical testing is planned.

A by-subject listing for ECG assessment results will be provided by subject ID number and visit in chronological order.

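### SAP safety tables are grouped by hepatic function only, so as written one Normal column mixes 30 mg and 10 mg controls; show Normal by dose as well

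*SAP*

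**What the plan says.** Every safety summary in the SAP names one grouping factor:

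- Adverse events (SAP 7.1.7): numbers and percentages "will be provided and summarized by SOC, PT, and hepatic function group as follows". SAP 7.1.8 then closes the subject: "No additional analysis of adverse events is planned".
- Numeric laboratory results (SAP 7.2.1): "Descriptive statistics will be provided by hepatic function group for each laboratory test specified in the study protocol".
- Graded laboratory abnormalities (SAP 7.2.2.2): summaries "will be provided by lab test and hepatic function group".
- Vital signs (SAP 7.3): "Descriptive statistics will be provided by hepatic function group for vital signs as follows".
- ECG shift table (SAP 7.5): results "compared with predose values will be presented by hepatic function group using the following categories".

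The protocol is similar. Under Protocol 8.6 the safety data "will be summarized by hepatic function group (according to the study drug received) using safety analysis set", and under Protocol 8.6.2 the treatment-emergent events "will be summarized by hepatic function group, system organ class, and preferred term".

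Other parts of the SAP name cohort as well. Disposition (4.1), demographics (5.1) and baseline characteristics (5.2) each ask for two layouts, one by hepatic function group and one by group inside each cohort. PK (8.3.1) and PD (9.3.1) are summarized by group inside each cohort.

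Dose follows cohort: 30 mg in Cohorts 1 and 2, 10 mg in Cohort 3 (SAP 1.3 and Table 8-1). SAP 1.3 lets a control serve more than one cohort only where those cohorts test the same dose.

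**The concern.** Each impaired severity received one dose, so the mild, moderate and severe columns are each homogeneous in dose. Normal is the only hepatic function level that spans both doses. A table with columns Normal, Mild, Moderate and Severe therefore sets the severe group, all on 10 mg, beside a reference drawn mostly from subjects on 30 mg. It also sets the mild and moderate groups, all on 30 mg, beside a reference that includes some 10 mg subjects.

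Safety and tolerability in the normal, mild, moderate and severe groups is a secondary objective. If adverse events depended on dose, the pooled column would describe neither set of controls, and a difference between severe and Normal could not be separated from the difference in dose. The tables would give the reader no same-dose control column to check against.

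**Working it through.** **The grouping.** Because SAP 4.1, 5.1 and 5.2 name both layouts, the SAP treats them as different things. Sections 7.1.7, 7.2.1, 7.2.2.2, 7.3 and 7.5 name only the first. Protocol 8.7 gives the group levels as normal, mild, moderate and severe, with cohort as a separate qualifier. Taken literally, the safety tables have one Normal column.

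**The plan's own figure.** No document states the size of the Normal column. The nearest planned figure is 10 per group, which reproduces: 8 evaluable × 1.25 = 10, and 10 × 6 groups = 60.

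**Controls at 10 mg.** 10 are planned (SAP text at Figure 1-1). Under the same-dose rule in SAP 1.3, none of them can come from Cohorts 1 or 2.

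**Controls at 30 mg.** Inputs: 37 enrolled as of 1 November 2017 (Protocol 1.2.5.2.1), and N=10 impaired and N=10 controls in each of Cohorts 1 and 2 (Protocol Table 1-3).

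- If the table and the count share a data cut and all 37 were in Cohorts 1 and 2: 37 − 20 = 17 distinct controls, so 20 − 17 = 3 were shared.
- If, in addition, the one subject who discontinued was impaired and was replaced: 37 − 21 = 16.
- If no control was shared: 20. This needs 20 + 20 = 40 subjects, more than 37. Table 1-3 carries no cut-off date in the available text, however, so later enrolment could have supplied the rest.
- If all controls were shared: 10. This is ruled out because the control means differ between the cohorts (AUCinf 3030 against 2810; Cmax 604 against 496).

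**Share of the Normal column on 10 mg** = n10 / (n30 + n10):

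| n30 | n10 | Pooled n | Share on 10 mg |
|---|---|---|---|
| 16 | 10 | 26 | 10/26 = 38% |
| 17 | 10 | 27 | 10/27 = 37% |
| 20 | 10 | 30 | 10/30 = 33% |

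**What pooling could do.** The pooled rate is (n30·p30 + n10·p10)/(n30 + n10), here with 17 and 10.

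- At the only dose-specific rates in the documents (Protocol 1.2.5.1, 4/15 at each dose), the pooled rate is 26.7%, the same as at either dose, so there is no distortion.
- At assumed rates of 30% on 30 mg and 10% on 10 mg, it is (5.1 + 1.0)/27 = 22.6%, which is 12.6 points above the 10 mg rate. These rates illustrate the mechanism and have no support in the documents.

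**Precision after the split.** One event is 1/10 = 10 percentage points in the 10 mg column, 1/17 = 5.9 in the 30 mg column and 1/27 = 3.7 in the pooled column. With no events, the one-sided 95% upper limit, 1 − 0.05^(1/n), is 25.9% for n = 10 and 10.5% for n = 27.

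**The case against.** The strongest objection is that pooling is inferred. No table shells are given. The SAP introduces its two groups inside each cohort, and SAP Table 8-1 lists the 30 mg and 10 mg regimens as separate treatments. The parenthesis in Protocol 8.6 could then mean a split by dose. That reading is possible but not clear. Both regimens are the same study drug, Protocol 8.2.1.1 uses similar language for subjects treated other than as assigned, and the SAP safety sections do not repeat the parenthesis, although SAP 7.7 reports no change from the protocol. So the columns still need to be stated.

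The second objection is that little turns on it, and most of this stands. The safety objective does not ask for a matched contrast; only the primary PK objective does. Safety is descriptive, with no formal testing planned for laboratory, vital-sign or ECG data. Laboratory and vital-sign changes are taken within subject. The disposition and exposure listings (SAP 4.1 and 4.2) let a reader recover cohort and dose.

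The equal rates of 4/15 also point to little distortion. They are weak evidence: the study was fasted and placebo-controlled, the rates cover single and multiple dosing, and the denominators are 15 for adverse events against 12 for PK.

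A reader might infer that the severe group's safety results will be biased, or that an excess of events will be hidden. The documents do not support that, because they show no dose effect on adverse events in controls at these doses.

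**Conclusion.** The point holds as a gap in table layout. As written, the safety summaries give one Normal column containing both doses, and no control column at the dose given to the severe group. Roughly one third of that column, about 33% to 38%, would be on 10 mg.

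The range assumes that Cohort 3 enrols its planned 10 controls, that the same-dose rule is followed, and that there are 16 to 20 distinct 30 mg controls. Protocol 3.1 allows sharing across cohorts without the same-dose limit, so it should be reconciled with the synopsis and SAP 1.3. A reader might take 17 controls and 37% as established. They are not: they depend on an undated preliminary table sharing the 1 November 2017 cut, and on all 37 subjects being in Cohorts 1 and 2. The second condition is supported, because Protocol 1.2.5.2 describes everyone as receiving 30 mg and Protocol 1.3.1 sets the 10 mg dose from Cohort 1 and 2 data.

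A reader might also carry the problem over to PK or PD. Those comparisons are made within cohort and are unaffected.

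The size and direction of any effect on safety rates cannot be estimated from the documents, and the likely effect is small. This is a cheap improvement that could be made.

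**What to change.** In SAP 7.1.7, 7.2.1, 7.2.2.2, 7.3 and 7.5, state the columns: Normal 30 mg, Normal 10 mg, Normal pooled, Mild, Moderate, Severe. Assign controls by dose received. Count each shared control once in the 30 mg column and once in the pooled column; under the same-dose rule no control can fall in both dose columns. Align Protocol 8.6 if it is amended for other reasons.

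Adding the within-cohort layout already used in SAP 4.1, 5.1 and 5.2 would also work, but each control shared by Cohorts 1 and 2 would then appear in two blocks.

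The cost is two extra columns and wider tables, with no new data. The 10 mg control column will hold only about 10 subjects, so its percentages will move in steps of 10 points and should be read with the counts. SAP section 1 says the plan is finalized before the database, so fixing the columns then avoids choosing them after the data are seen.
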